Primary Efficacy Analysis: The primary efficacy endpoint for Part 1 is the percent change in frequency of seizures that result in drops (DSF: drop seizure frequency) per 28 days between the T+M and Baseline periods in Cohort A. The DCF will be calculated from all available data collected during the Baseline and treatment periods without imputation. The percent change in DSF will be calculated as the change in DSF between T+M and Baseline / DSF during Baseline \times 100. Both the mean and median percent change in DCF frequency will be presented. The primary endpoint will be assessed using a non-parametric rank analysis of covariance (ANCOVA) with treatment and weight groups (<37.5 kg, \geq 37.5 kg) as factors, and with Baseline MCDS as a covariate rank baseline DSF as a

ZX008 (Fenfluramine Hydrochloride)**ZX008-1601 Clinical Study PA 4.0 (Japan) 25 July 2022**

covariate, and rank percent change in DSF from baseline as the response variable. The primary analysis will compare the ZX008 0.8 mg/kg/day group to the placebo group at the $\alpha=0.05$ level of significance. The difference between the ZX008 0.8 mg/kg/day and placebo groups in percent change in DSF, and its 95% confidence interval, will be estimated using the Hodges-Lehmann method. As a sensitivity analysis, the primary endpoint will also be analyzed using a parametric ANCOVA that incorporates treatment group and weight group as factors, log baseline DSF as a covariate; and log DSF during T+M as the response variable. Another sensitivity analysis will use a Wilcoxon rank-sum test to compare the ZX008 0.8 mg/kg/day group to the placebo group. Part 1 Cohort B will be analyzed using analogous methods.

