In Study 1504 Cohort 2, subjects randomized to ZX008 0.5 mg/kg/day had a median baseline convulsive seizure frequency 14.0 compared to 10.7 for subjects randomized to placebo. Subjects randomized to ZX008 0.5 mg/kg/day achieved a 54.0% reduction compared to placebo ($P < 0.001$).

Controlling for multiplicity with a hierarchical testing procedure, all key secondary endpoints were met in both studies, for ZX008 0.8 mg/kg/day and 0.2 mg/kg/day groups (Study 1) and ZX008 0.5 mg/kg/day (Study 1504 Cohort 2). In Study 1, the proportion of subjects achieving a $\geq 50\%$ reduction from Baseline in CSF was 67.5% for the ZX008 0.8 mg/kg/day group, and 38.5% for the 0.2 mg/kg/day group, with both groups being statistically significantly different from placebo (12.5%; $P < 0.001$ and $P = 0.009$, respectively). In Study 1504 Cohort 2, 53.5% of subjects randomized to ZX008 0.5 mg/kg/day compared to 4.5% of subjects randomized to placebo achieved a $\geq 50\%$ reduction from Baseline in CSF ($P < 0.001$).

The proportion of subjects with a $\geq 50\%$ reduction in monthly convulsive seizure frequency was also highly statistically significant for all ZX008 dose groups compared to placebo, with 38.5%, 53.5%, and 67.5% of subjects in the 0.2 mg/kg/day, 0.5 mg/kg/day, and 0.8 mg/kg/day cohorts achieving $\geq 50\%$ reduction as compared to 8.3% in placebo. Additionally, in Study 1, subjects randomized to ZX008 0.2 and 0.8 mg/kg/day had a median 15- and 25-day convulsive seizure-free interval, respectively, compared to 9.5 days for placebo ($P = 0.035$ and $P < 0.001$). In Study 1504 Cohort 2, subjects randomized to ZX008 0.5 mg/kg/day had a median 22-day convulsive seizure-free interval compared to 13 days for placebo ($P < 0.004$).

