3.2 NUMBER OF SUBJECTS

Approximately 340 subjects will be screened to obtain 250 subjects randomized into Part 1 Cohort A (75 subjects per treatment arm), and at least 30 (and up to 50) subjects will be randomized into Part 1 Cohort B. The number of screened subjects may exceed 340 depending on the screen fail rate. Each clinical site will not randomize more than a maximum of 15 subjects without prior consent from the sponsor.

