10.1.1 DETERMINATION OF SAMPLE SIZE

The sample size for Part 1 Cohort A was estimated under the assumption that adding ZX008 at 0.8 mg/kg/day to current therapy will lead to a mean decrease in drop seizures that is 30 percentage points greater than adding placebo to current therapy. For example, if adding placebo leads to a 10% decrease in seizures, then adding the high dose of ZX008 would be expected to decrease seizures by at least 40%.

The variability expected in the trial was estimated from a Phase 3 trial of clobazam for patients with Lennox-Gastaut syndrome (Ng 2011) leading to an assumption that the SD is 50%. Other assumptions include an allowance for 20% dropouts between randomization and the start of the maintenance period.

Under these assumptions, and using a Wilcoxon rank-sum test to approximate the primary comparison between the ZX008 0.8 mg/kg/day and placebo groups, a sample size of 63 subjects per treatment group affords 90% power to detect a difference between groups that is significant at the $\alpha=0.05$ level. Assuming a 20% drop-out rate prior to the start of the maintenance period yields a requirement for an additional 16 subjects per group for a total of 79 subjects per treatment group. Similar calculations for the 0.2 mg/kg/day ZX008 group lead to a total required sample size of 237. The number of subjects randomized into Part 1 Cohort A is estimated to be approximately 250 due to the long baseline period.

The sample size of 10 to 15 subjects per treatment group in Cohort B is expected to provide a descriptive assessment of whether the treatment effect in Japanese subjects is similar that observed in Cohort A subjects from the rest of the world.

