The first key secondary endpoint for the ZX008 0.8 mg/kg/day group – the proportion of subjects who achieve a \geq 50% reduction from baseline in the frequency of seizures that result in drops – is derived directly from the primary endpoint, but is widely considered a benchmark for clinical meaningfulness of a medical intervention for seizures. The comparison will be made using a logistic regression model that incorporates the same factors and covariate as the ANCOVA used in the primary analysis. The second key secondary endpoint – the proportion of

ZX008 (Fenfluramine Hydrochloride)
ZX008-1601 Clinical Study PA 4.0 (Japan) 25 July 2022

subjects assessed by the Investigator as minimally, much, or very much improved on the CGI-I will be analyzed using a Cochran-Mantel-Haenszel test (CMH) stratified by weight strata.

The percent change from baseline DSF in the ZX008 0.2 mg/kg/day group will be compared to the placebo group using the same methods employed for the primary analysis. In particular, the same ANCOVA model will be used. Nonparametric methods will be used if normality assumptions do not hold. Analyses of other key secondary endpoints involving the ZX008 0.2 mg/kg/day group will employ similar methods as those used to compare ZX008 0.8 mg/kg/day to placebo.

Multiplicity Strategy and Testing Hierarchy

The efficacy analyses will employ a serial gatekeeper strategy to maintain the Type 1 error rate at $\alpha=0.05$ across the family of analyses that support the primary and key secondary objectives. The strategy specifies a hierarchy of significance tests where each test acts as a gatekeeper to the tests below it.

The hierarchy starts with the primary analysis comparing ZX008 0.8 mg/kg/day to placebo on the percent change from baseline in DSF. The next two steps in the hierarchy also entail comparisons of ZX008 0.8 mg/kg/day to placebo on two key secondary endpoints. The last three steps in the hierarchy all involve comparisons of ZX008 0.2 mg/kg/day to placebo.

Below is a complete list of steps in the testing hierarchy in order:

1. Compare ZX008 0.8 mg/kg/day to placebo on the percent change in DSF from baseline in DSF.
2. Compare ZX008 0.8 mg/kg/day to placebo on the proportion of subjects who achieve a $\geq 50\%$ reduction from baseline in DSF.
3. Compare ZX008 0.8 mg/kg/day to placebo on the change from baseline in the number of all countable motor seizures.

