4. Compare ZX008 0.2 mg/kg/day to placebo on the percent change from baseline in DSF.
5. Compare ZX008 0.2 mg/kg/day to placebo on the proportion of subjects who achieve a $\geq 50\%$ reduction from baseline in the DSF.
6. Compare ZX008 0.2 mg/kg/day to placebo on the CGI-I at Visit 12.

Part 1 Cohort B

Efficacy analyses for Part 1 Cohort B will use the same methods as described for Part 1 Cohort A. Some subsets analyses may not be feasible in Cohort B due to its smaller sample size.

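### Cohort B (10 to 15 per arm) inherits Cohort A's adjusted logistic regression for the 50% responder endpoint, with no provision for an arm without responders, where an ordinary fit gives no finite odds ratio or Wald interval

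*Protocol*

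**What the plan says.** Section 10.1.6.1 describes the Cohort A responder analysis: "The comparison will be made using a logistic regression model that incorporates the same factors and covariate as the ANCOVA used in the primary analysis". In that ANCOVA these are treatment group, weight group (below 37.5 kg, or 37.5 kg and above) and baseline drop seizure frequency (DSF), entered as a rank.

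The same section then sets the rule for Japan: "Efficacy analyses for Part 1 Cohort B will use the same methods as described for Part 1 Cohort A". Its one exception is that some subset analyses may be infeasible because the cohort is small. The synopsis (Statistical Methods, primary efficacy analysis) is looser: "Part 1 Cohort B will be analyzed using analogous methods".

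On size, section 10.1.1 says: "The sample size of 10 to 15 subjects per treatment group in Cohort B is expected to provide a descriptive assessment". Section 3.2 says that "at least 30 (and up to 50) subjects will be randomized into Part 1 Cohort B", which at 1:1:1 is 10 to about 17 per arm.

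The protocol names neither an estimation method nor a test for the logistic model. It gives no fallback for an arm without responders. Section 10.1.6 refers the full methods to a SAP that is not shown.

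**The concern.** The protocol recognises that Cohort B is small, but the exception it makes covers subset analyses only. It leaves in place a model that can break down in the main comparison. With no responders on placebo, the likelihood keeps rising as the treatment coefficients grow, so the odds ratios of the doses against placebo have no finite estimate.

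Cohort B exists to show whether the effect in Japanese subjects resembles that in Cohort A, and section 10.1.6.1 itself presents the 50% responder rate as a benchmark of clinical meaningfulness. An estimate with a usable interval is what that comparison needs. If the prescribed model fails, a substitute would have to be chosen after the data are seen.

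**Working it through.** **Plan's own figures.** The protocol gives no operating figure for the Cohort B responder model. Its arm size can be checked: 30/3 = 10, and 10 to 15 per arm is 30 to 45 in total. The section 3.2 ceiling of 50 gives 50/3 = 16.7, about 17.

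**Inputs**
- Placebo 50% responder rates (section 1.3, convulsive seizures in Dravet syndrome): 12.5% in Study 1, 4.5% in Study 1504 Cohort 2, and a pooled figure given as "reduction as compared to 8.3% in placebo".
- Lennox-Gastaut planning example (section 10.1.1): placebo mean decrease 10%, SD 50%. No responder rate for Lennox-Gastaut syndrome is stated.

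**Responder rate implied by the planning example.** Assuming normally distributed percent change, P(reduction of at least 50) = P(Z ≥ (50 − 10)/50) = P(Z ≥ 0.8) = 21.2%.

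**Chance that the placebo arm has no responders**, (1 − p)^n:

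| Placebo rate p | n = 10 | n = 15 | n = 17 |
|---|---|---|---|
| 4.5% | 0.955^10 = 63% | 50% | 46% |
| 8.3% | 0.917^10 = 42% | 27% | 23% |
| 12.5% | 0.875^10 = 26% | 13% | 10% |
| 21.2% (planning example) | 0.788^10 = 9% | 3% | 2% |

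At the Study 1 responder rates for the active arms (38.5% and 67.5%), an empty active arm has a chance under 1%.

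**What the fit does with an empty placebo arm.** Ordinary maximum-likelihood fits with treatment, weight group and rank baseline were run on two-arm data. The Wald and likelihood-ratio columns are medians over 200 random covariate sets.

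| Placebo vs active | Wald P | Likelihood-ratio P | Fisher exact P |
|---|---|---|---|
| 0/10 vs 5/10 | 0.9999 | 0.0035 | 0.033 |
| 0/15 vs 7/15 | 0.9998 | 0.0005 | 0.006 |

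The treatment coefficient drifted to about 26 when iteration stopped, with a standard error above 100,000. Neither figure means anything beyond non-convergence.

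The exact values follow by hand: 2 × C(10,5)/C(20,5) = 2 × 252/15,504 = 0.033, and 2 × C(15,7)/C(30,7) = 2 × 6,435/2,035,800 = 0.006.

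**Separation through the covariates.** An empty arm is not the only route to failure, because treatment, weight group and baseline together can also separate responders from non-responders. Simulations with baseline unrelated to response found no finite fit in about 3% to 37% of trials. The low end is the planning example at 15 per arm; the high end is Study 1 rates at 10 per arm with one dose against placebo.

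**The case against.** The strongest reply is that the protocol says only that a logistic regression will be used. It does not say maximum likelihood, it does not name a Wald test, and a SAP could specify a penalised or exact fit without contradicting it. That is correct, so a reader should not infer that the plan obliges the sponsor to use a method that fails. What stands is that the protocol states a positive rule, same methods with only subsets excepted, and that an unqualified logistic regression is ordinarily read as the standard fit.

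A reader might also infer that a strong effect would be reported with a P value near 1. That is true of the Wald test only; the likelihood-ratio test on the same data gives a small P value. The infinite odds ratio remains whichever test is used.

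A reader might take the event to be likely. The high probabilities rest on Dravet convulsive-seizure rates. The protocol's own Lennox-Gastaut planning figures give 9% or less. Nor does an empty placebo arm by itself signal a large effect: 0/10 vs 2/10 fails in the same way.

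Finally, little information would be lost. Section 10.1.6 has categorical data summarised by cohort as frequencies and percentages, so 5/10 against 0/10 would be visible. Section 10.1 compares the cohorts descriptively. This limits the consequence and is accepted.

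Extending the point to the weight-stratified CMH test for CGI-I is not supported: that test pools over strata, and no failure has been shown.

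**Conclusion.** The point holds as a limited one. Section 10.1.6.1 carries an adjusted logistic model to 10 to 15 subjects per arm, and the ordinary fit of that model has no finite odds ratio or Wald interval if an arm has no responders. The chance of that on placebo runs from about 3% (planning example, 15 per arm) to 63% (4.5% rate, 10 per arm). The planning-example figure assumes normality; the others assume that Dravet rates carry over to Lennox-Gastaut syndrome, which the documents do not establish. All assume independent binomial responders. The event is therefore plausible, and common enough at the lower placebo rates to be planned for.

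The effect is confined to a descriptive cohort. The primary endpoint, which uses Cohort A only, and the Cohort A responder analysis are untouched.

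**What to change.** In section 10.1.6.1, for Cohort B only, replace the logistic model by responder proportions per arm and each dose's difference from placebo with an exact confidence interval. If an adjusted odds ratio is still wanted, specify Firth-penalised logistic regression with penalised-likelihood intervals, which stay usable with an empty arm. Align the synopsis sentence on Cohort B with section 10.1.6.1 so that both state the same rule, and carry it into the SAP.

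The cost is a sentence or two and standard software. The one downside is that the exact comparison is not adjusted for weight group or baseline DSF. Cohort A methods stay as they are.

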10.1.6.2 Safety Analyses

Summaries of safety data will be presented by treatment – ZX008 0.8 mg/kg/day, ZX008 0.2 mg/kg/day or placebo – for the T+M period. The number and percentage of subjects in each treatment group with AEs will be displayed by body system and preferred term using the Medical Dictionary for Regulatory Activities (MedDRA). Summaries of AEs by severity and relationship to study drug will also be presented. A separate summary will be provided for all

ZX008 (Fenfluramine Hydrochloride)
ZX008-1601 Clinical Study PA 4.0 (Japan) 25 July 2022

serious AEs (SAEs). If warranted, selected summaries will be repeated broken out by weight group, ie, for subjects who weigh <37.5 kg and those who weigh ≥37.5 kg.

Laboratory tests, vital signs, physical examinations, neurological examinations, ECG, Doppler echocardiogram, C-SSRS, Tanner Staging results, etc, will be summarized appropriately, by treatment. All safety summaries will be based on the SAF Population.

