| Adverse events of special interest | X ^a | | | | X | | X ^l | |

AED=antiepileptic drug; BMI=body mass index; C=Collect; CBD=cannabidiol; D=Dispense; ECG=electrocardiogram; EOS=end of study; ET=early termination; HADS=Hospital Anxiety and Depression Scale; BRIEF=Behavior Rating Inventory of Executive Function; QoL=quality of life; R=Review;

a: Use data collected at Visit 12 of Part 1.

b: At the discretion of the investigator, Visit 16 may be conducted as a phone visit.

c: Or early termination.

d: Safety Follow-up visits will be conducted for subjects who terminate early from Part 2 and for those who complete Part 2. Standard follow-up visits should occur 3 and 6 months after the last dose. If there are any findings at a post-dose follow-up, a follow-up visit will be scheduled every 3 months until resolved or stabilized.

e: Use Part 1 Visit 12 information unless complete neurological examination is warranted based on significant changes in subject status.

ZX008 (Fenfluramine Hydrochloride)
ZX008-1601 Clinical Study PA 4.0 (Japan) 25 July 2022

| Study Assessments – PART 2 | OLE Treatment Period** | | | | | | Post-Dosing | Cardiac Follow-up |
|----------------------------|------------------------|-----------------------|--|------------------------|--|-----------------------------------|-------------|-------------------|
| Visit Number | Visit 15 ^a | Visit 16 ^b | Visits 17-21 (Months 1, 2, 3, 6 and 9 ^{**}) | Visit 22 (Month 12) | Visits 23-41 (Months 15, 18, 21, 24, 27, 30, 33, 36, 39, 42, 45, 48, 51, 54, 57, 60, 63, 66, 69) | Visit 42 ^c (EOS/ET) | Visit 43 | Visit 44 and 45 |

- f: ECHOs will be performed at Months 1, 3, 6, and 9.
- g: The Months 3, 6, 9, 12, 18, 21, 24, 27, 30, 33, 36, 39, 42, 45, 48, 51, 54, 57, 60, 63, 66, 69 & 72 ECHO may be performed any time within 3 weeks prior to the study visit. If a subject discontinues early from the study, the ECHO should be scheduled as soon as practical.
- h: Females of child-bearing potential
- i: For Visit 15, use data collected at Part 1 Visit 12 unless clinical laboratory evaluation is warranted based on significant changes in subject status. For Visit 16, clinical laboratory evaluation is optional based on subject status.
- j: Visit 20 only.
- k: For subjects who are transitioning to commercial drug, do not initiate drug taper or conduct post-dosing and cardiac follow-up visits.
- l: Only adverse events related to cardiac safety will be collected at this visit.

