5.5.5 Part 1: Transition Period

Subjects who complete the Maintenance Period and will be continuing into the open-label extension (Part 2) will be transitioned from double-blind study medication to open-label ZX008 (Table 7).

All subjects entering the open-label extension (Part 2) will be transitioned from their blinded daily dose to the 0.2 mg/kg dose during the 2-week interval between Visits 12 and 15, without breaking the blind. The IWR system will assign two bottles of IMP to the subject, one for each step in the transition. A new bottle of IMP will be started by the subject at each level of the transition step. See Section 5.1 for more information about the volume of ZX008 or placebo to be administered.

Table 7: Transition Algorithm for Part 1

| Dose Group in Double-Blind Study | Transition Step 1 Day 1-4 after Visit 12 | Transition Step 2 Days 5-14 after Visit 12 |
|---|---|---|
| ZX008 0.2 mg/kg/day | ZX008 0.2 mg/kg/day | ZX008 0.2 mg/kg/day |
| ZX008 0.8 mg/kg/day (0.5 mg/kg/day for subjects taking concomitant STP) | ZX008 0.4 mg/kg/day | ZX008 0.2 mg/kg/day |
| Placebo | ZX008 0.2 mg/kg/day | ZX008 0.2 mg/kg/day |

Note: maximum daily dose of ZX008 is 30 mg (or 20 mg for subjects taking concomitant STP).

Subjects who had been randomized to placebo increase their dose to 0.2 mg/kg/day beginning on Day 1 of the transition. The first dose should be taken in the clinic during Visit 12. Subjects will be required to stay in the clinic for monitoring of adverse reactions until the investigator determines it is safe to leave. Those considered by the investigator to need further monitoring will be hospitalized until the investigator determines they can be safely discharged. Subjects who had been randomized to 0.2 mg/kg/day will continue to receive that dose. Subjects who had been randomized to 0.8 mg/kg/day or were receiving the maximum dose of 30 mg/day (or subjects taking concomitant STP and randomized to 0.5 mg/kg/day; 20 mg/day maximum) decrease to a dose of ZX008 0.4 mg/kg/day, or a maximum of 30 mg/day (20 mg/day for subjects taking concomitant STP). After 4 days at this dose level (Day 5), these subjects will decrease their dose to 0.2 mg/kg/day. Subjects will report to the clinic on Day 14 for enrollment into the open-label extension.

ZX008 (Fenfluramine Hydrochloride)
ZX008-1601 Clinical Study PA 4.0 (Japan) 25 July 2022

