6.2.1 Clinic Visit 15 (OLE Study Day 1)

Part 2 Visit 15 will occur 14 days (± 4 days) after Part 1 Visit 12. The 14-day transition period preceding Visit 15 may be extended up to 14 days in the case of a required safety adjudication of a Visit 12 ECHO alert.

The following procedures will be performed during Visit 15:

- Ensure entry criteria for Part 2 are met
- Vital signs
- Record prior and concomitant medications (use core study Visit 12 information)
- Instruct parent/caregiver on use of diary
- Record ongoing AEs as medical history
- Record ongoing AESI as medical history
- Collect, review, and dispense diary (after above procedures have been concluded)
- Dispense study medication

Data collected from Part 1 Visit 12 may be used for the following procedures unless otherwise indicated:

- Record medical, neurological, and epilepsy history
- Complete physical examination, including height and weight (use data collected at Part 1 Visit 12, unless there was a significant change in subject status warranting a new complete examination)
- Complete neurological examination (use data collected at Part 1 Visit 12, unless there was a significant change in subject status warranting a new complete examination)

ZX008 (Fenfluramine Hydrochloride)
ZX008-1601 Clinical Study PA 4.0 (Japan) 25 July 2022

- 12-lead ECG
- Doppler ECHO
- Laboratory evaluation (serum chemistry, hematology, immunoglobulin, hormones, and urinalysis) (use Part 1 Visit 12 information, unless investigator determines new laboratory evaluation is warranted due to change in subject status) (if collecting urine for urinalysis, urine may be collected at home, the night before the clinic visit, as long as collection procedures are followed to maintain sample stability)
- Pregnancy test
- Urine or serum THC panel
- Whole blood CBD
- C-SSRS Since Last Visit Assessment ([Appendix 2](#))
- CGI-I (assessed by parent/caregiver)
- CGI-I (assessed by investigator)
- BRIEF ([Appendix 3](#))
- QOLCE ([Appendix 6](#))
- HADS ([Appendix 7](#))
- Zarit Caregiver Burden Inventory ([Appendix 8](#))

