8.4 OBSERVATION PERIOD FOR ADVERSE EVENT REPORTING

The observation period for AE and SAE reporting in an individual subject will start at the time

ZX008 (Fenfluramine Hydrochloride)
ZX008-1601 Clinical Study PA 4.0 (Japan) 25 July 2022

of giving written informed consent for participation in the current study and finish 15 days after the last dose of study drug or the last visit, whichever is later. For subjects who enroll in the open-label extension (Part 2), ongoing AEs will be followed in that study.

If the investigator becomes aware of an SAE that has started after the observation period has finished, and the event could in some way be associated with IMP (irrespective of whether or not it is considered by the investigator to be causally related to IMP), then this must also be reported to the sponsor (see [Section 8.6](#)).

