10.1.5 TREATMENT PERIODS

Baseline Period

The Baseline Period covers the 28 days immediately prior to randomization. The baseline frequency of seizures that lead to drops will be calculated from data collected during this period.

Titration Period

The Titration Period covers the first 14 days of treatment while subjects are titrated to their randomized dose. It begins on the first full day of treatment (Study Day 1) and extends through Study Day 15 regardless of the exact day on which a subject reaches his or her assigned dose. The Titration Period applies to all subjects including placebo recipients.

Maintenance Period

The Maintenance Period covers the 12 weeks following the end of the titration period. It begins on Study Day 16 and extends through Study Day 99.

Titration +Maintenance (T+M) Period

The T+M period combines the Titration and Maintenance periods, beginning on Study Day 1 and extending through Study Day 99. The T+M period is considered the treatment period.

Taper/Transition Period

The Taper/Transition Period begins immediately at the end of T+M period and extends to Visit

ZX008 (Fenfluramine Hydrochloride)
ZX008-1601 Clinical Study PA 4.0 (Japan) 25 July 2022

13, 2 weeks later; ie, from Study Day 99 through Study Day 113.

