10.2.3 TREATMENT PERIODS

Open-Label Extension (OLE) Treatment Period

The OLE Treatment Period covers the duration during which subjects receive open label treatment with ZX008.

OLE Taper Period

The OLE Taper Period begins immediately after the OLE Treatment period and extends for 2 weeks.

ZX008 (Fenfluramine Hydrochloride)
ZX008-1601 Clinical Study PA 4.0 (Japan) 25 July 2022

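### The planned safety summaries skip the blinded transition, in which placebo subjects entering Part 2 first take ZX008, and the Part 1 period definitions contradict each other around it

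*Protocol*

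**What the plan says.** **Part 1 safety.** Section 10.1.6.2 states: "Summaries of safety data will be presented by treatment – ZX008 0.8 mg/kg/day, ZX008 0.2 mg/kg/day or placebo – for the T+M period".

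**Part 1 periods.** Section 10.1.5 has T+M "beginning on Study Day 1 and extending through Study Day 99" and the Taper/Transition Period running "from Study Day 99 through Study Day 113". It describes titration as 14 days but ends it on Day 15, and gives maintenance as Days 16 to 99. Section 3.1 gives T+M as 14 weeks, and Table 5 ends titration on Day 14.

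**The transition.** Section 5.5.5 says: "Subjects who had been randomized to placebo increase their dose to 0.2 mg/kg/day beginning on Day 1 of the transition". The first transition dose is taken in clinic at Visit 12, which Table 9 places on Day 99 ± 4. The 0.8 mg/kg/day arm steps down in two stages over the same interval (Table 7). The medication is still blinded (Section 5.5.1.1; Synopsis, Duration of Treatment).

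**Part 2 safety.** The safety population is those dosed during the open-label extension (Section 10.2.1.1). Section 10.2.3 adds: "The OLE Treatment Period covers the duration during which subjects receive open label treatment with ZX008". Section 10.2.4.1 tabulates treatment-emergent AEs. OLE Study Day 1 is Visit 15, 14 ± 4 days after Visit 12, and the transition can be extended by up to 14 days for an ECHO alert (Section 6.2.1, Table 11).

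**AE recording at Visit 15.** Section 6.2.1: "Record ongoing AEs as medical history". The Visit 15 entry in the Adverse Events row of Table 2 carries footnote a: "Use data collected at Visit 12 of Part 1". Section 8.4 says that for subjects who enrol in Part 2 "ongoing AEs will be followed in that study".

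**The concern.** Section 10.1.5 defines a Taper/Transition Period, but neither safety analysis section uses it. Part 1 summaries stop at the end of T+M and Part 2 summaries start with open-label dosing. The interval between them is when former placebo subjects begin ZX008. The protocol itself treats that first dose as needing supervision: it is given in clinic, with monitoring and hospitalisation if needed. It then plans no summary of the days that follow.

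Long-term safety and tolerability is the primary objective of Part 2 (Section 2.2.1). An event that starts on ZX008 during the transition and is still present at Visit 15 enters Part 2 as history. It would then probably not be tabulated as emerging on ZX008, and early-onset effects in the newly exposed subjects could be under-reported.

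The second issue is that T+M ends on a fixed study day while the switch to transition medication is tied to the actual date of Visit 12. Some transition days can therefore be counted as randomised treatment in the primary endpoint.

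**Working it through.** **1. The plan's sample size.** Inputs from Section 10.1.1: difference 30 points, SD 50, α = 0.05 (sidedness not stated; two-sided assumed), power 90%. A two-sample t-test needs 60 per arm. Dividing by the Wilcoxon efficiency 3/π gives 60 × π/3 = 62.8, so 63. Then 63/0.8 = 78.75, so 79, and 3 × 79 = 237. The plan's figures reproduce; power at 63 per arm is 90.4%.

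**2. Period lengths.** 14 weeks × 7 = 98 days, but Days 1 to 99 are 99 days. Titration on Days 1 to 15 is 15 days, not 14. Maintenance on Days 16 to 99 is 84 days = 12 × 7. So the surplus day is in titration, and it pushes the end of T+M onto Day 99, the day on which Taper/Transition also begins.

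**3. Where the 14 transition days fall.** Transition days inside T+M = max(0, 99 − v + 1), where v is the day of Visit 12. The rest, up to the day before Visit 15, are in no planned safety summary. With Visit 15 exactly 14 days after Visit 12:

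| Visit 12 | Visit 15 | Transition days inside T+M | Transition days in no summary |
|---|---|---|---|
| Day 95 | Day 109 | 5 (5/99 = 5.1%) | Days 100–108 = 9 |
| Day 99 | Day 113 | 1 (1/99 = 1.0%) | Days 100–112 = 13 |
| Day 103 | Day 117 | 0 | Days 103–116 = 14 |

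A full ECHO-alert extension on schedule gives 13 + 14 = 27 days. On Day 99 itself, part of the day precedes the clinic dose.

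**4. How many subjects.** Allocation is 1:1:1, so placebo is 250/3 ≈ 83 in Cohort A, and 30/3 = 10 to 50/3 ≈ 17 in Cohort B. These are ceilings, reached only if every placebo subject enters Part 2. If the arms enter at similar rates, about one third of entrants are affected.

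**5. Effect on the primary contrast.** Shift in a placebo subject's percent change = assumed immediate effect of ZX008 0.2 mg/kg/day × overlap days / 99. The documents do not give that immediate effect, so 10 to 60 points is an assumed range. Power is the Wilcoxon approximation at 63 per arm, with the 30-point difference reduced by the shift:

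| Assumed effect | Shift, 1 day | Power | Shift, 5 days | Power |
|---|---|---|---|---|
| 10 | 0.1 | 90.2% | 0.5 | 89.4% |
| 30 | 0.3 | 89.8% | 1.5 | 87.3% |
| 60 | 0.6 | 89.2% | 3.0 | 83.5% |

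The five-day columns need every placebo subject to attend on Day 95 and enter Part 2, so they are an extreme bound. The step-down of the 0.8 mg/kg/day arm on the same days is not included; it works in the same direction.

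**The case against.** The best defence is that Section 10.1.6.2 names T+M without saying that nothing else will be summarised. Its paragraph on laboratory tests, ECG and ECHO names no period. Section 10.1.6 leaves the full description to the SAP, and the protocol never defines treatment-emergent. A SAP could add a transition table and a suitable emergence rule. This limits the point but does not remove it. The protocol is not silent: it states a window that leaves out first exposure, and it gives sites a recording instruction that the SAP does not control.

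A reader might infer that safety data are lost, or that these events could appear nowhere. The documents do not support that. AEs are observed from consent until 15 days after the last dose or the last visit, whichever is later (Section 8.4), and SAEs are reported throughout (Section 8.6). An event ongoing at Visit 15 is already on the Part 1 record. Listing it as history can coexist with following it in Part 2. Section 6.2.1 also places AE recording among the procedures done at Visit 15, not among those that may use Visit 12 data. The three passages need reconciling more than they flatly conflict.

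A reader might also infer that the transition generally contaminates the placebo arm's efficacy data. On schedule it is part of one day, and with a late Visit 12 it is nothing. Section 10.1.5 also has Taper/Transition begin at the end of T+M, so the day numbers can be read as nominal.

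A third inference is that taper and off-drug diary days of early terminators are counted in T+M. That needs T+M to run on to Day 99 after treatment stops. Section 10.1.5 calls T+M the treatment period and has taper start at its end. Section 10.1.2.2, in a garbled sentence, ties the primary comparison to at least four weeks of maintenance diary data. No size can be put on that reading.

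**Conclusion.** The safety point stands on the text. On schedule, 13 days of blinded transition lie outside every planned safety summary. For former placebo subjects, about one third of Part 2 entrants if the arms enter at similar rates, these are nearly all of the first fortnight on ZX008. The gap is in planned summaries and in Part 2 classification, not in data collection. That events would be missed as treatment-emergent is likely from the medical-history instruction, but not certain, because the term is undefined here.

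The period definitions in Section 10.1.5 are wrong as written: 15 days for a 14-day titration, 99 days for 14 weeks, and Day 99 in two periods. The consequence for the primary endpoint is small and conservative, since it makes placebo look better and the high dose worse. With a 30-point immediate effect, the shift is 0.3 points on schedule and 1.5 points if every placebo subject attends on Day 95. The sample size is unaffected. This should be corrected, but it does not threaten the primary result.

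**What to change.** **Safety**
- Add a Taper/Transition summary by randomised arm and by treatment actually received, so that events on ZX008 in former placebo subjects are not labelled as placebo events.
- For subjects randomised to placebo, count ZX008 exposure and treatment-emergent AEs from the first transition dose. For the two active arms, count Part 2 emergence from the start of the transition, not from their first Part 1 dose, which would pull all of Part 1 into Part 2.
- At Visit 15, keep the original onset date of every ongoing AE, and reconcile Section 6.2.1, Table 2 footnote a and Section 8.4.

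**Periods**
- Define Titration as Days 1–14 and Maintenance as Days 15–98 (14 + 84 = 98), with T+M ending on the day before the first taper or transition dose. This removes the shared Day 99 and settles the treatment of early terminators.

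**Cost.** Protocol wording, an eCRF completion note and extra tables. Part 2 AE rates may rise slightly. One caution: Section 3.6 describes enrolment up to June 2019, and this amendment is dated July 2022. If the Cohort A primary analysis has already been run, keep it as it is, report the corrected T+M window as a sensitivity analysis, and apply the corrected definitions to analyses still to come.
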